1.3.4 Predicting Remission of Suicidal Ideation

Baseline Prediction: In relation to target engagement, we used TMS-EEG to identify the neurophysiological predictors of decreased suicidal ideation associated with MST treatment[68]. We applied single and paired pulse TMS-EEG to the left DLPFC at baseline prior to MST treatment in 27 TRD patients. Our recently published study[68]demonstrated that the amplitude of the N100 and the extent of LICl in frontal and central midline region significantly correlated with remission of suicidal ideation based on the Scale for Suicidal Ideation[69]. This relationship was specific to the DLPFC and was not observed when N100 and LICl were assessed in the motor cortex. Additionally, we demonstrated that N100 and LICl in the frontal cortex predicted remission of suicidal ideation with 90% sensitivity and 89% specificity[68].

Target engagement: LICl was derived from the left DLPFC in 20 TRD patients prior to and after a course of MST treatment. Change in LICl predicted remission of suicidal ideation correctly with 85.7% sensitivity and 100% specificity (AUC = 0.98, p = 0.002). This pilot data suggests that LICl is modified by MST and that individualized changes in LICl by MST may underlie the differential treatment response for suicidal ideation.

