3.0 OBJECTIVES AND HYPOTHESES

Primary objective: To assess the efficacy and cognitive adverse effects of MST compared to RUL-UB ECT in patients with depression.

Primary hypothesis/combined effectiveness endpoint: (1) MST will result in remission rates on the 24-item Hamilton Rating Scale for Depression (HRSD-24) that is non-inferior to that of RUL-UB ECT; **AND** (2) MST will have a superior cognitive adverse effect and tolerability profile compared to RUL-UB ECT as assessed with the Autobiographical Memory Test (AMT).

Secondary objective: To assess the efficacy MST compared to RUL-UB ECT in ameliorating suicidal ideation in patients with depression.

Secondary hypothesis/effectiveness endpoint: MST will have a non-inferior remission rate on the SSI compared to RUL-UB-ECT in patients with depression.

Tertiary objective: To refine and develop candidate neurophysiological biomarker, cortical inhibition (CI), using combined transcranial magnetic stimulation and electroencephalography (TMS-EEG) that may predict response to treatment using remission of suicidal ideation as a meaningful clinical indicator.

Tertiary hypothesis/effectiveness endpoint: (1) Change in CI in the DLPFC following MST will significantly predict SSI reduction; (2) Following MST and ECT, increased complexity in course time scales derived through multi-scale entropy will be associated with change in the AMT scores in patients with depression.

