5.8.4 Tertiary Outcome Analysis: Neurophysiological Data

We will investigate the relationship between change in CI and SSI reduction by calculating the area under the receiver operating characteristic (ROC) curve (AUC) as discussed above (Section 1.3.4). ROC analysis is used in medicine to evaluate diagnostic test accuracy. The ROC involves plotting the sensitivity (true positive rate) versus 1-specificity (false positive rate). The ROC AUC predicts performance of the diagnostic test. An AUC of 1 represents perfect prediction with optimal sensitivity and specificity while 0.5 suggests that the diagnostic test is no better than chance at diagnostic prediction. For our purposes, the ROC AUC then corresponds to the change in CI that optimally distinguishes MST and ECT remitters from non-remitters (defined as a zero score on the SSI). Based on our preliminary data described above (Section 1.3.4), we will use change in CI (defined as the LICl TMS-EEG response) to distinguish MST and ECT SSI remitters from non-remitters using a ROC AUC of >0.85 on all frontal electrodes using a false detection rate correction that is applied to all frontal electrodes.

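### Sections 5.8.4 and 5.8.5 treat the ROC AUC as an optimal marker value and plan no internal validation, so any cut-off derived from the curve would look better than it is

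*Combined protocol and SAP*

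**What the plan says.** Section 5.8.4 plans to relate change in CI, measured as the LICI response on TMS-EEG, to remission on the SSI "by calculating the area under the receiver operating characteristic (ROC) curve (AUC) as discussed above (Section 1.3.4"). After a general description of ROC curves it states that "the ROC AUC then corresponds to the change in CI that optimally distinguishes MST and ECT remitters from non-remitters". The success criterion follows: remitters are to be separated "using a ROC AUC of >0.85 on all frontal electrodes using a false detection rate correction that is applied to all frontal electrodes".

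Section 5.8.5 repeats the construction for memory, equating the AUC with a baseline level of multi-scale entropy. It sets the same 0.85 threshold across frontal electrodes and mentions no multiplicity correction.

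Section 1.3.4, to which 5.8.4 refers, gives pilot results mainly as sensitivity and specificity. In 27 patients with baseline measures these were 90% and 89%. In a further analysis LICI was "derived from the left DLPFC in 20 TRD patients prior to and after a course of MST treatment", and "Change in LICl predicted remission of suicidal ideation correctly with 85.7% sensitivity and 100% specificity", with an AUC of 0.98. Section 1.4.1 also describes the biomarker by its sensitivity and specificity.

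**The concern.** The AUC is the probability that a randomly chosen remitter has a more favourable marker value than a randomly chosen non-remitter. It has no units of CI change or entropy and points to no particular value. A value that best separates two groups is a cut-off, which is a different quantity needing its own rule. The plan runs the two together and gives no rule.

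If an analyst resolves this by taking the best point on the observed curve and quoting its sensitivity and specificity, those figures are optimistic, because the cut-off was tuned to the same participants. The correction across electrodes in 5.8.4 concerns significance and does not remove this. The only bootstrap in the plan, in 5.8.1, is for the adjusted difference in remission rates.

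At stake is the accuracy attached to the biomarker. The tertiary objective in section 3.0 is to develop a candidate predictor, and section 1.4.1 envisages using such a marker to identify patients likely to benefit. Accuracy at a tuned cut-off would not be matched in the next patients.

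**Working it through.** The documents give no sample size, cut-off or optimism figure for the ROC analyses, so there is no plan figure to reproduce. The size is found by simulation.

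**Inputs from the documents.** Total sample 260 (5.7.1). Remission about 60% (5.8.2). The number with paired TMS-EEG is not stated and may be below 260: section 5.5 lets patients without biomarker testing continue in the clinical portion, and section 8.5 makes neurophysiology conditional on hospital directives.

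**Assumptions.** Paired recordings 100 to 260; true AUC 0.70; normally distributed marker with equal variance in remitters and non-remitters; cut-off chosen to maximise J = sensitivity + specificity - 1.

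**Step 1, true separation.** The standardised difference is d = √2 × Φ⁻¹(AUC) = 1.414 × 0.524 = 0.742. The best attainable J is 2Φ(d/2) - 1 = 2Φ(0.371) - 1 = 2 × 0.645 - 1 = 0.29.

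**Step 2, optimism.** In each simulated trial the best cut-off is chosen in the sample, and its apparent J is compared with the true J of that same cut-off. With one electrode and 260 recordings, J is reported as 0.33 against a true 0.28. With 100 it is 0.36 against 0.27. Mean excess in J is below; paired values come from two separate runs.

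| Paired recordings | One electrode | Best of 15, correlation 0.6 | Best of 15, correlation 0.9 |
|---|---|---|---|
| 260 | 0.054; 0.058 | 0.123; 0.118 | 0.097 |
| 150 | 0.076; 0.074 | 0.158; 0.161 | 0.127 |
| 100 | 0.096; 0.093 | 0.192; 0.191 | 0.159 |

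The 15 electrodes and their correlations are assumed.

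**Step 3, other scales.** The mean of sensitivity and specificity carries half the excess: 0.054/2 = 0.027 and 0.096/2 = 0.048, about 3 to 5 points for one electrode. As percent correctly classified, the excess is about 2-3 points at 260 and 4-5 at 100.

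**Step 4, the AUC itself.** For one pre-specified electrode, mean optimism in the AUC was zero within ±0.4 points at every sample size from 20 to 260. If the best electrode is picked, the AUC is inflated by about 2 to 6 points at 260 to 100 recordings.

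**Step 5, sensitivity.** Over true AUC 0.70 to 0.85, the one-electrode excess in J is 4-6 points at 260, 8-10 at 100 and 11-14 at 50. Prevalence matters little: at AUC 0.85 and 260 recordings it is 4.3 points with 40% remitters and 4.2 with 60%.

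These sizes are for 5.8.4. The same mechanism applies in 5.8.5, but the proportion with memory decline is not given, so no separate figure is offered.

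**The case against.** The strongest reply is that the plan's measure is the AUC and its only criterion is an AUC above 0.85. An AUC needs no cut-off, so choosing one cannot inflate it. That stands, and step 4 confirms it. A reader might infer that the 0.85 criterion is itself biased by the confused sentence; for a pre-specified electrode it is not. Applying the criterion in new patients is also a genuine test of the pilot result.

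Second, neither section says that a cut-off will be chosen, scored or reported. This is also fair: the step is an inference. It is a strong one, because an optimally separating change in CI can only be a threshold, and the pilot figures to which 5.8.4 refers are sensitivities and specificities, which exist only at a threshold. Even without a cut-off, the sentences need correcting.

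Third, a reader might take the upper figures, near 19 points, as the bias to expect. The documents do not support that. They do not say that the best electrode will be selected; the wording refers to all frontal electrodes, without saying whether each, any or an average must pass 0.85. The figures are also on the J scale and should not be read as percent correctly classified.

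Fourth, a reader might conclude that the pilot accuracies were themselves inflated. Section 1.3.4 does not say whether they were validated, so that cannot be judged.

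Finally, the analysis is tertiary and exploratory in purpose, and touches neither the primary nor the secondary conclusion. That limits the weight of the point.

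**Conclusion.** The point holds in a limited form. Sections 5.8.4 and 5.8.5 confuse the AUC with an optimal marker value and plan no internal validation of the ROC analyses. The AUC of a pre-specified electrode is unaffected.

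If a best cut-off is derived and scored on the same participants, J is overstated by about 5 points with 260 paired recordings, rising to about 10 with 100. If the best frontal electrode were selected as well, the excess in J would be about 10 to 20 points, and the AUC would be inflated too.

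The sizes depend on an unstated biomarker sample size, a true AUC of 0.70, the equal-variance normal model and, for the larger range, an assumed 15 electrodes correlated 0.6 to 0.9. Severity is low.

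**What to change.** Replace the two sentences in 5.8.4 and 5.8.5. State that the AUC, with a confidence interval, measures overall discrimination, and say how the 0.85 criterion applies across frontal electrodes. State the expected number of participants with paired recordings.

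If a cut-off is to be reported, pre-specify its rule. Derive it, and any electrode choice, inside repeated 10-fold cross-validation or with bootstrap optimism correction, and report only the corrected sensitivity and specificity as the marker's accuracy. Leave-one-site-out validation is an alternative only where site numbers allow: section 7.1.1 adds the third site in March 2022, and the enrolment projections in 7.1.2 cover the other two. If one pre-specified electrode is used with no fitted model, its AUC needs only the interval.

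The cost is SAP wording and slightly more analysis work, with no new data or visits. The reported accuracy will be somewhat less favourable.

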5.0 APPROACH

5.1.1 Research Design and Methods

The trial will be registered in an international clinical trial registry (clinicaltrials.gov) and results will be reported in a manner consistent with the international CONSORT guidelines. The study will involve a randomized, double blind, parallel-group clinical trial with two treatment arms conducted at three leading academic institutions in North America: CAMH, University of Texas Southwestern in Dallas, and University of California, San Diego (UCSD). Based on our power analysis (Section 5.7.1), a total of 260 participants with depression will be randomized to receive MST or RUL-UB-ECT. We plan to enroll four to five participants per month across the three study sites over 54 months.

Treatment will be administered two to three days per week. Depression symptoms will be assessed with the 24-item Hamilton Depression Rating Scale (HRSD-24) [74] and suicidality will be assessed with the Scale for Suicidal Ideation (SSI) [69]. Remission will be defined as HRSD-24 ≤ 10 and a $> 60\%$ decrease in scores from baseline on two consecutive ratings. Once a participant reaches remission, a second rating to confirm remission will be conducted immediately before their next scheduled treatment. If remission is confirmed, they will then be considered a completer of the acute treatment course. Remission of suicidal ideation is defined as a score of 0 on the SSI. Therefore, there will be no specific minimum number of treatments that patients must receive to be classified as remitters. However, patients who do not meet remission criteria after 21 treatment sessions will be considered non-remitters and will cease treatment sessions. This maximum treatment number was chosen allowing for the possibility that MST may require more treatment sessions to achieve remission, similar to RUL-UB ECT [29-31]. The blind will not be broken to participants until the completion of the entire study. Following completion of the acute treatment course, participants who achieve response (defined as a 50% reduction in symptoms on the HRSD-24 from baseline) or remission will be referred to a maintenance treatment trial.

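### Tertiary hypothesis (1) claims significant prediction of SSI reduction after MST, but Section 5.8.4 offers only an AUC threshold of 0.85 for SSI = 0 using both arms, so the hypothesis has no matching test

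*Combined protocol and SAP*

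**What the plan says.** Section 3.0, tertiary hypothesis (1): "Change in CI in the DLPFC following MST will significantly predict SSI reduction". The tertiary objective just above it is framed differently. It seeks a biomarker that "may predict response to treatment using remission of suicidal ideation as a meaningful clinical indicator", and Section 5.1.1 fixes that indicator: "Remission of suicidal ideation is defined as a score of 0 on the SSI".

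Section 5.8.4 opens with the hypothesis's outcome: "We will investigate the relationship between change in CI and SSI reduction by calculating the area under the receiver operating characteristic (ROC) curve". It then specifies a ROC analysis for SSI = 0, in which change in CI (the LICI response on TMS-EEG) is to "distinguish MST and ECT SSI remitters from non-remitters using a ROC AUC of >0.85 on all frontal electrodes". Multiplicity over electrodes is covered by one phrase only: "using a false detection rate correction that is applied to all frontal electrodes". The same section notes that an AUC of "0.5 suggests that the diagnostic test is no better than chance at diagnostic prediction".

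The threshold is said to rest on the preliminary data in Section 1.3.4: 20 patients treated with MST, AUC 0.98, p = 0.002.

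**The concern.** The hypothesis and its analysis differ in three respects.

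- **Outcome.** The hypothesis concerns SSI reduction; the analysis concerns a final score of 0. A fall from 25 to 2 is a large reduction without remission. Section 5.1.2 sets no minimum SSI for entry, so a participant at 0 before and after treatment would count as a remitter with no reduction.
- **Population.** The hypothesis is about change after MST; the analysis covers MST and ECT.
- **Criterion.** Significant prediction means an AUC distinguishable from 0.5. An AUC above 0.85 is a much higher bar, and it is set on the point estimate.

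Section 5.8.4 names a multiplicity correction, but not the p-values it corrects, their null hypothesis or the error level. Nor does it say whether every frontal electrode or any one must exceed 0.85. A moderate but real association could therefore be reported as confirming or as not confirming the hypothesis, and the choice could be made after the data are seen.

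**Working it through.** **The plan's own figure.** The 0.85 threshold comes with no derivation, power statement or biomarker sample size, so it cannot be reproduced. The check is how far it lies from a significance criterion.

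**Inputs**
- Null AUC 0.5 (Section 5.8.4).
- Remission about 60%. Section 5.8.2, on the SSI endpoint, gives this for both treatments.
- Number with paired TMS-EEG: not stated. Sections 5.5 and 8.5 allow it to fall below the trial total. I assume 60, 130 (one full arm, Section 5.7.1) and 260 (both arms).
- Assumed: two-sided 0.05; one electrode; no electrode correction unless stated.

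**Step 1: smallest AUC significant against 0.5.** With n1 remitters, n2 non-remitters and N = n1 + n2, the Mann-Whitney null standard error is √[(N+1)/(12·n1·n2)]. The smallest significant AUC is 0.5 + 1.96 × that value.

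- N = 60 (36/24): √(61/10,368) = 0.0767; 0.5 + 0.150 = **0.65**
- N = 130 (78/52): √(131/48,672) = 0.0519; 0.5 + 0.102 = **0.60**
- N = 260 (156/104): √(261/194,688) = 0.0366; 0.5 + 0.072 = **0.57**

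A Bonferroni bound for an assumed 10 electrodes (multiplier 2.807) raises these to about 0.72, 0.65 and 0.60. The zone between significance and 0.85 narrows but remains wide.

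**Step 2: how often each criterion is met.** Binormal simulation, 4,000 runs, 60% remitters, one electrode. The mean shift is √2·Φ⁻¹(true AUC).

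| True AUC | N = 130: significant | N = 130: AUC > 0.85 | N = 60: AUC > 0.85 | N = 260: AUC > 0.85 |
|---|---|---|---|---|
| 0.70 | 0.98 | <0.001 | 0.01 | <0.001 |
| 0.75 | 1.00 | 0.006 | 0.05 | 0.001 |
| 0.80 | 1.00 | 0.10 | 0.21 | 0.03 |
| 0.85 | 1.00 | 0.51 | 0.53 | 0.52 |
| 0.90 | 1.00 | 0.96 | 0.88 | 0.99 |
| 0.98 | 1.00 | 1.00 | 1.00 | 1.00 |

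**Step 3: cross-check by formula.** Hanley-McNeil variance at A = 0.75, N = 130: Q1 = A/(2−A) = 0.600 and Q2 = 2A²/(1+A) = 0.643. The variance is [0.1875 + 77(0.600−0.5625) + 51(0.643−0.5625)]/(78·52) = 7.17/4,056 = 0.00177, so the standard error is 0.042. Then (0.85−0.75)/0.042 = 2.38, an upper tail of about 0.9%. This agrees with the simulated 0.6%.

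**Reading.** Below a true AUC of 0.85 the criteria usually disagree once the association is significant. At 0.85 the threshold is about an even chance. Well above 0.85 they agree. If every frontal electrode must exceed 0.85, the threshold is stricter than these one-electrode figures show.

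**The case against.** Four points on the other side carry weight.

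- **No failure rule is written.** A reader might infer that a significant relation would usually be recorded as a failed hypothesis. Section 5.8.4 never says that an AUC of 0.85 or less means failure, and its multiplicity correction implies p-values, so a significance criterion may be intended. Usually is also wrong at the only effect size the documents give for CI change: at 0.98 the threshold is essentially always passed. That value comes from 20 patients treated with MST, with no interval, and may be optimistic, but it cannot be ignored.
- **Remission is a stated target.** The tertiary objective names remission of suicidal ideation, so a ROC for SSI = 0 is a legitimate analysis, and SSI reduction may be loose wording. This stands for the objective. The hypothesis and the opening sentence of Section 5.8.4 still say reduction, and nothing analyses it.
- **The role of baseline SSI is not shown.** A reader might also infer that the SSI = 0 outcome largely reflects baseline SSI. The documents give no baseline distribution, so this cannot be claimed. The examples under the concern show only that the two outcomes can differ.
- **A discrimination target suits a biomarker meant to guide treatment.** True: significance against 0.5 is a weak bar for clinical use. That supports keeping 0.85 as a benchmark, not letting it stand in for the hypothesis test.

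**Conclusion.** The point holds as a mismatch between hypothesis and analysis. Section 3.0 states a significance claim on SSI reduction after MST. Section 5.8.4 gives a point-estimate threshold for SSI = 0 using both arms and leaves the hypothesis without a defined test.

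If 0.85 is used as the criterion, observed AUCs from about 0.60 (N = 130) or 0.65 (N = 60) up to 0.85 satisfy the hypothesis and miss the threshold, and the plan does not say how such a result is judged. The size rests on the assumed biomarker numbers, 60% remitters, a binormal model, one electrode and no electrode correction. That the criteria differ does not depend on these assumptions.

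The primary and secondary conclusions, the trial's sample size and safety are unaffected. The change is still worth making before the data are analysed.

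**What to change.** In Section 5.8.4:

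1. **Test of hypothesis (1).** In the MST arm, relate post-treatment SSI to change in LICI with baseline SSI as covariate. Use a method suited to many zero scores, such as a rank-based or ordinal model. Apply the planned false-detection-rate correction to these p-values, and state its level and the set of frontal electrodes.
2. **Both arms.** Analyse MST and ECT together as a secondary analysis with a treatment term.
3. **Remission objective.** Keep the ROC for SSI = 0. Report each AUC with its 95% interval and a test against 0.5.
4. **Threshold.** Label 0.85 a benchmark for clinical usefulness, not the test of the hypothesis, and say whether it applies to each frontal electrode or to any.

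The cost is SAP wording and one extra regression. Table 1 in Appendix A already schedules SSI and TMS-EEG at baseline and after the acute phase, so no new data are needed. The drawbacks are that the headline is no longer a single AUC and that the main test uses only the MST participants with paired recordings, about 130 at most under the planned allocation.

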5.8.5 Multi-scale entropy analysis

For this hypothesis, we will follow the analytic methods described in section 5.4. We will investigate the relationship between complexity in course time scales derived through multi-scale entropy and change in the AMT scores in patients with depression. The ROC AUC will correspond to the level of multi-scale entropy at baseline that optimally distinguishes MST and ECT memory performance using a receiver operator area under the curve of >0.85 across all frontal electrodes.

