1.3.5 Predicting ECT-Induced Cognitive Impairment through Multi-Scale Entropy

Additional data from our group suggests that resting EEG can be used to predict cognitive adverse effects following a course of seizure therapy. We obtained resting-state EEG from 34 patients receiving MST or ECT, and employed multi-scale entropy to quantify the complexity of brain temporal dynamics before and after seizure therapy. Temporal complexity represents the temporal fluctuations in resting state neurophysiological signals. The more complex the signal, the less recurring temporal patterns it contains. In ECT, but not MST, complexity of brain temporal dynamics in coarse time scales was significantly increased. In a subset of 19 patients we obtained scores of global cognitive function using the Montreal Cognitive Assessment (MoCA)[70] before and after ECT (n = 6) and MST (n =13) treatment. We found that increased complexity in coarse time scales derived through multi-scale entropy from EEG predicted change in MoCA with over 90 percent accuracy.

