5.4. Resting EEG and Multi-Scale Entropy

Ten minutes of resting-state eyes closed EEG data are recorded prior to the start and after a course of ECT or MST treatment. EEG will be through a 64-channel NeuroScan EEG system. Acquired data will be imported into MATLAB (The MathWorks. Inc. Natick, MA, USA) for preprocessing. The open source signal processing functions in EEGLAB toolbox will be used for data import and preprocessing. Multi-scale entropy will be examined across all electrodes using two steps [101]: The *coarse-graining* process and the calculation of the sample entropy (*SampEn*) for each coarse-grained time series. First, for a given time series $\{x_1, x_2, \dots, x_N\}$, the multiple coarse-grained time series $\{y_1^{(\tau)}, y_2^{(\tau)}, \dots, y_N^{(\tau)}\}$ at scale factor τ are calculated by averaging the data points within non-overlapping windows of increasing length τ . Each element of the coarse-grained time series $y_j^{(\tau)}$, will be calculated as $y_j^{(\tau)} = \frac{1}{\tau} \sum_{i=(j-1)\tau+1}^{j\tau} x_i$, where τ represents the scale factor and $j \left(1 \leq j \leq \frac{N}{\tau}\right)$ represents the time index of the element. The length of each coarse-grained time series is M , where $M = \text{floor} \left(\frac{N}{\tau}\right)$. Second, the degree of predictability is measured for each of the multiple coarse-grained time series $\{y_1^{(\tau)}, y_2^{(\tau)}, \dots, y_N^{(\tau)}\}$ using SampleEn. SampleEn is calculated as $\text{SampleEn}(r, m, M) = -\ln(C(m+1)/C(m))$, where $C(m)$ is the total number of pairs of m consecutive similar data points, $C(m+1)$ is the total number of pairs of $m+1$ consecutive similar data points in the multiple coarse-grained time series. SampleEn quantifies the variability by estimating the predictability of amplitude patterns across a time series. Two consecutive data points will be used for data matching ($m = 2$) and data points will be considered to match if their absolute amplitude difference is less than 0.15% ($r = 0.15$) of standard deviation of time series. Multi-scale entropy will be calculated for two 20s continuous epochs according to Farzan et al. and then averaged [102].

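### Tertiary hypothesis 2 concerns the rise in EEG complexity, but the Section 5.8.5 ROC uses baseline entropy; if entropy change is analysed, randomised arm belongs in the analysis

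*Combined protocol and SAP*

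**What the plan says.** Tertiary hypothesis 2 in Section 3.0 reads: "Following MST and ECT, increased complexity in course time scales derived through multi-scale entropy will be associated with change in the AMT scores". The predictor is a rise after treatment, and the two arms are named together.

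Section 5.8.5 opens: "We will investigate the relationship between complexity in course time scales derived through multi-scale entropy and change in the AMT scores in patients with depression". It then gives one operational rule, a ROC whose area is to correspond to "the level of multi-scale entropy at baseline that optimally distinguishes MST and ECT memory performance", judged "using a receiver operator area under the curve of >0.85 across all frontal electrodes". The section gives no model, arm term, stratification, interaction or significance level, and it does not define the binary AMT outcome that a ROC needs.

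Either predictor could be computed, because Section 5.4 states: "Ten minutes of resting-state eyes closed EEG data are recorded prior to the start and after a course of ECT or MST treatment".

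On what treatment does to the predictor, the pilot in Section 1.3.5 reports: "In ECT, but not MST, complexity of brain temporal dynamics in coarse time scales was significantly increased". It gives no effect size and no test between arms. The pilot link to cognition used the MoCA, not the AMT, in 19 patients measured "before and after ECT (n = 6) and MST (n =13) treatment", and is summarised as one accuracy figure.

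On what treatment does to the outcome, the second half of the primary hypothesis in Section 3.0 expects the AMT to favour MST. Stage 2 of Section 5.8.1 defines deterioration as a worsening of at least 25% on the AMT total score.

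**The concern.** There are two linked problems. First, the hypothesis and the analysis name different predictors. A ROC on pre-treatment entropy may show whether baseline complexity predicts memory loss, but it cannot show whether an increase in complexity goes with memory loss.

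Second, an analyst who tests the hypothesis as written will use entropy change. If the arms are combined without regard to treatment, arm can act as a common cause of both variables. ECT participants would tend to have larger entropy rises and more AMT worsening, MST participants less of each, and the combined data would show an association even if entropy change carried no information about memory within either arm. The risk is that a difference between treatments is reported as a neurophysiological marker of memory loss. The artefact grows with the AMT difference that the trial hopes to show.

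**Working it through.** **Inputs from the plan.** 130 participants per arm; a between-arm AMT difference that I read as 25 percentage points; significance level 0.05 for the primary calculation (all Section 5.7.1); AUC threshold 0.85 (Section 5.8.5).

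**Assumptions, because the plan gives no figure.** Entropy change is normal and larger with ECT by d = 0.5, 0.8 or 1.0 within-arm SD. AMT worsening (ECT/MST) is 35%/10%, 45%/20% or 55%/30%, with 35%/20% as a smaller case. The number with EEG is 260, 130 or 60, since Section 5.5 lets participants continue without biomarker testing and Section 8.5 restricts neurophysiology during the pandemic. One entropy summary per participant is tested, two-sided at 5%. Entropy and AMT worsening are independent within each arm.

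**Step 1: the plan's own AMT figure.** Power for two proportions is Φ{[0.25 − 1.96·√(2p̄(1−p̄)/130)] / √([p₁(1−p₁) + p₂(1−p₂)]/130)}. For 35% v 10%, p̄ = 0.225 and this is Φ{(0.25 − 1.96 × 0.0518)/0.0494} = Φ(3.00) = 0.9987. For 62.5% v 37.5% it is 0.984. The stated power above 95% is reproduced, so 25 points is a fair reading of the difference the trial is built to detect.

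**Step 2: pooled AUC created by arm alone.** With equal arms, let a = p_E/(p_E + p_M) be the ECT share of those who worsen and b = (1−p_E)/[(1−p_E) + (1−p_M)] the ECT share of those who do not. Then AUC = 0.5 + (a − b)·[Φ(d/√2) − 0.5].

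For 35%/10%: a = 0.778, b = 0.419, a − b = 0.358.
- d = 0.5: 0.5 + 0.358 × 0.138 = 0.550
- d = 0.8: 0.5 + 0.358 × 0.214 = 0.577
- d = 1.0: 0.5 + 0.358 × 0.260 = 0.593
- Complete separation of the arms: 0.5 + 0.358/2 = 0.679

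Across the three 25-point settings the range is 0.535 to 0.593 for d = 0.5 to 1.0, with a ceiling of 0.63 to 0.68. Passing 0.85 takes something like 60% v 0% with complete separation (0.857).

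**Step 3: rejection rates with no within-arm relation.** Rank test, 2,000 simulated trials per setting; Monte Carlo standard error at 5% is √(0.05 × 0.95/2000) = 0.5 points.

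| EEG participants | AMT worsening ECT/MST | Pooled change, d = 0.5 | d = 0.8 | d = 1.0 | Stratified by arm |
|---|---|---|---|---|---|
| 260 | 35/10 | 20% | 44% | 60% | 5% |
| 260 | 45/20 | 17% | 36% | 48% | 4–5% |
| 260 | 55/30 | 17% | 35% | 45% | 5% |
| 260 | 35/20 | 10% | 18% | 25% | 5–6% |
| 130 | 35/10 | 12% | 24% | 31% | 4–5% |
| 60 | 35/10 | 7% | 13% | 16% | 4–6% |
| 60 | 35/20 | 6% | 8% | 9% | 5% |

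A pooled test on baseline entropy with 260 participants rejects in 4% to 6%. An AUC above 0.85 occurred in at most 1 run of 2,000 in any setting.

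**Step 4: continuous AMT change.** If arm shifts entropy change by d₁ and AMT change by d₂ SD, the correlation from arm alone is ρ = (d₁d₂/4)/√[(1 + d₁²/4)(1 + d₂²/4)]. With d₂ = 0.5 (assumed), d₁ = 0.5 gives ρ = 0.0625/1.0625 = 0.059, and d₁ = 1.0 gives 0.125/1.152 = 0.108. Rejection at N = 260, 1 − Φ(1.96 − atanh(ρ)·√257), is about 16% and 42%.

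**The case against.** The strongest reply is that Section 5.8.5 does state a rule, and that rule is immune. Baseline entropy is measured before treatment, so randomisation makes it independent of arm. This stands. A reader might infer that the ROC as written is confounded by treatment; it is not.

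A reader might also infer that arm alone could make the marker pass its own test. It could not plausibly do so: the artefact gives AUCs of about 0.54 to 0.59 against a threshold of 0.85. Section 5.8.5 sets no separate significance test, so the exposure is confined to a claim of association, which is nevertheless what hypothesis 2 asserts.

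Pooling is not stated. It is the natural reading, since both arms are named together in the hypothesis and the analysis refers to patients with depression generally, but the ROC sentence could also mean analysis by arm or a contrast of arms.

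The pilot does not establish that the arms differ on complexity. A significant rise in one arm and none in the other is not a between-arm test, and the AMT difference is still a hypothesis.

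Finally, entropy change arises after randomisation, and Section 1.3.1 offers quantitative EEG as a probe of how ECT impairs cognition. If entropy change lies on that pathway, the between-arm part of the association is partly signal, and adjusting for arm answers a narrower question. This is a fair point about the estimand. It supports showing the components separately, not relying on the pooled figure alone.

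**Conclusion.** The concern holds in a limited form, and its severity is minor. The ROC in Section 5.8.5 does not test tertiary hypothesis 2, because one uses baseline level and the other an increase. If the hypothesis is tested with entropy change and the arms are combined, treatment alone can produce a significant association: about 17% to 60% of trials with 260 participants and a 25-point AMT difference, 10% to 25% with a 15-point difference, and 7% to 16% with 60 EEG participants and 25 points. With 60 participants and 15 points the excess is small. Stratifying by arm restores about 5% throughout.

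These rates rest on assumed entropy shifts, AMT rates and EEG numbers. The documents do not support extending the point to the baseline ROC, to the 0.85 criterion, or to any primary or secondary conclusion. Nor do they show that an arm-adjusted estimate is the only legitimate one.

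**What to change.** - Reconcile Sections 3.0 and 5.8.5 on the predictor: entropy change, baseline entropy, or both as separately labelled analyses.
- Define the binary AMT outcome for the ROC. The worsening of at least 25% already used in Stage 2 would serve.
- For the entropy-change analysis, include randomised arm in the model or use an arm-stratified AUC. Report within-arm estimates and an arm-by-entropy term beside any pooled estimate.
- State that a marker of memory loss will not be claimed from the pooled association alone.

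The cost is plan wording and one or two model terms on data already collected. There is a small loss of precision, and the between-arm component, which may reflect mediation, has to be reported separately.
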